	Primary endpoint of stroke (ischemic or hemorrhagic) and systemic embolism.	Measured 1 day after drug initiation in primary diagnosis position specified below and inpatient care setting: Stroke: ICD-9 discharge diagnosis codes: 430.xx Subarachnoid hemorrhage (SAH) 431.xx Intracerebral hemorrhage (ICH) 433.x1 Occlusion and stenosis of precerbral arteries with cerebral infarction 434.xx (excluding 434.x0) Occlusion and stenosis of cerebral arteries with cerebral infarction 436.x Acute, but ill-defined cerebrovascular events Systemic embolism: ICD-9 discharge diagnosis code: 444.xx Arterial embolism ICD-10 discharge diagnosis code: I74.x Arterial embolism and thrombosis	
For stroke: PPV of 85% or higher for ischemic stroke PPV ranging from 80% to 98% for hemorrhagic stroke →[Andrade SE, Harrold LR, Tjia J, et al. A systematic review of validated methods for identifying cerebrovascular accident or transient ischemic attack using administrative data. Pharmacoepidemiology and Drug Safety 2012;21 Suppl 1:100-28.] →[Tirschwell DL, Longstreth WT, Jr. Validating administrative data in stroke research. Stroke; a journal of cerebral circulation 2002;33:2465-70.] →[Roumali CL, Mitchell E, Gideon PS, Varas-Lorenzo C, Castellsague J, Griffin MR. Validation of ICD-9 codes with a high positive predictive value for incident strokes resulting in hospitalization using Medicaid health data. Pharmacoepidemiology and drug safety 2008;17:20-6.]
	Can't be measured in claims but not important for the analysis
		INCLUSION CRITERIA		
1	Men or women aged ≥18 years	Measured on the day of drug initiation: Age >=18		
2	Non-valvular Atrial fibrillation Atrial fibrillation must be documented by ECG evidence (e.g., 12-lead ECG, rhythm strip, Holter, pacemaker interrogation) within 30 days before randomization. In addition, subjects must have medical evidence of atrial fibrillation within 1 year before and at least one day before the qualifying ECG evidence. This could be obtained from a notation in the subject's record (e.g., medical chart, hospital discharge summary).	Measured 12 months prior to and including day of drug initiation, with >2 diagnoses separated by at least 14 days, in any diagnosis position and inpatient or outpatient care setting: Atrial fibrillation: ICD-9 diagnosis: 427.31 ICD-10 diagnosis: I48.0x, I48.1x, I48.2x, I48.9x		

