3	Non-valvular Atrial fibrillation Subjects with newly diagnosed atrial fibrillation are eligible provided that: - there is evidence that the atrial fibrillation is non-valvular - cardioversion is not planned - there is ECG evidence on 2 occasions 24 hours apart demonstrating atrial fibrillation			
	For Inclusion Criteria 4 It is either A) History of ischemic stroke or TIA or arterial embolism -OR- B) 2 of the following 4 1) Heart failure 2) Hypertension 3) Age >=75 4) Diabetes			
4	History of prior ischemic stroke, TIA or non-CNS systemic embolism believed to be cardioembolic in origin	Measured any time prior to and including day of drug initiation in any diagnosis position and inpatient or outpatient care setting: Ischemic stroke: ICD-9 diagnosis: 433.x, 434. x, 436.xx TIA: ICD-9 diagnosis: 435.xx Systemic embolism: ICD-9 diagnosis: 444.xx	
Patorno, Elisabetta et al. "Cardiovascular outcomes associated with canagliflozin versus other non-gliflozin antidiabetic drugs: population based cohort study." BMJ 2018;360:k119 http://dx.doi.org/10.1136/bmj.k119
 
Patorno, Elisabetta et al. "Empagliflozin and the Risk of Heart Failure Hospitalization in Routine Clinical Care: A First Analysis from the Empagliflozin Comparative Effectiveness and Safety (EMPRISE) Study." Circulation. 2019 Apr 8. doi: 10.1161/CIRCULATIONAHA.118.039177
	
	OR 2 or more of the following risk factors	Measured anytime prior to and including day of drug initiation in any diagnosis position and inpatient or outpatient care setting:		
4a	– Heart failure and/or left ventricular ejection fraction ≤35%	Heart failure: ICD-9 diagnosis: 428.x, 398.91, 402.01, 402.11, 402.91, 404.01, 404.11, 404.91, 404.03, 404.13, 404.93	
Patorno, Elisabetta et al. "Cardiovascular outcomes associated with canagliflozin versus other non-gliflozin antidiabetic drugs: population based cohort study." BMJ 2018;360:k119 http://dx.doi.org/10.1136/bmj.k119
 
Patorno, Elisabetta et al. "Empagliflozin and the Risk of Heart Failure Hospitalization in Routine Clinical Care: A First Analysis from the Empagliflozin Comparative Effectiveness and Safety (EMPRISE) Study." Circulation. 2019 Apr 8. doi: 10.1161/CIRCULATIONAHA.118.039177
	

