...Midwest; n (%)	1,900 (21.2%)	1,902 (21.3%)	0.00	3,502 (31.0%)	3,436 (30.4%)	0.01	8,521 (27.4%)	8,630 (27.8%)	-0.01	13,923 (27.1%)	13,968 (27.2%)	0.00				
...West; n (%)	2,459 (27.5%)	2,496 (27.9%)	-0.01	1,619 (14.3%)	1,608 (14.2%)	0.00	4,714 (15.2%)	4,737 (15.5%)	0.00	8,792 (17.1%)	8,841 (17.2%)	0.00				
...Unknown+missing; n (%)	N/A	N/A	#VALUE!	56 (0.5%)	63 (0.6%)	-0.01	N/A	N/A	#VALUE!	56 (0.5%)	63 (0.6%)	-0.01				
CV Covariates																
Ischemic heart disease; n (%)	3,345 (37.4%)	3,391 (37.9%)	-0.01	4,174 (36.9%)	4,143 (36.7%)	0.00	13,673 (44.0%)	13,547 (43.6%)	0.01	21,192 (41.3%)	21,081 (41.1%)	0.00				
Acute MI; n (%)	283 (3.2%)	286 (3.2%)	0.00	335 (3.0%)	321 (2.8%)	0.01	1,279 (4.1%)	1,279 (4.1%)	0.00	1897 (3.7%)	1886 (3.7%)	0.00				
ACs/unstable angina; n (%)	260 (2.9%)	272 (3.0%)	-0.01	329 (2.9%)	314 (2.8%)	0.01	1,247 (4.0%)	1,204 (3.9%)	0.01	1836 (3.6%)	1790 (3.5%)	0.01				
Old MI; n (%)	511 (5.7%)	520 (5.8%)	0.00	367 (3.2%)	368 (3.3%)	-0.01	2,737 (8.8%)	2,639 (8.5%)	0.01	3615 (7.0%)	3527 (6.9%)	0.00				
Stable angina; n (%)	482 (5.4%)	502 (5.6%)	-0.01	456 (4.0%)	438 (3.9%)	0.01	1,541 (5.0%)	1,478 (4.8%)	0.01	2,479 (4.8%)	2,418 (4.7%)	0.00				
Coronary atherosclerosis and other forms of chronic ischemic heart disease; n (%)	3,067 (34.3%)	3,086 (34.4%)	0.00	3,851 (34.1%)	3,793 (33.6%)	0.01	12,563 (40.4%)	12,456 (40.1%)	0.01	19,481 (38.0%)	19,335 (37.7%)	0.01				
Other atherosclerosis with ICD10 v2 Copy; n (%)	142 (1.6%)	152 (1.7%)	-0.01	210 (1.9%)	212 (1.9%)	0.00	545 (1.8%)	561 (1.8%)	0.00	897 (1.7%)	925 (1.8%)	-0.01				
Previous cardiac procedure (CABG or PTCA or Stent)																
v4; n (%)	119 (1.3%)	70 (0.8%)	0.05	164 (1.5%)	94 (0.8%)	0.07	581 (1.9%)	386 (1.2%)	0.06	864 (1.7%)	550 (1.1%)	0.05				
History of CABG or PTCA; n (%)	862 (9.6%)	877 (9.8%)	-0.01	539 (4.8%)	614 (5.4%)	-0.03	4,822 (15.5%)	4,833 (15.6%)	0.00	6,223 (12.1%)	6,324 (12.3%)	-0.01				
Any stroke; n (%)	1,763 (19.7%)	1,721 (19.2%)	0.01	2,030 (18.0%)	2,018 (17.9%)	0.00	6,768 (21.8%)	6,728 (21.7%)	0.00	10,561 (20.6%)	10,467 (20.4%)	0.00				
Ischemic stroke (w and w/o mention of cerebral infarction); n (%)	1,763 (19.7%)	1,721 (19.2%)	0.01	2,030 (18.0%)	2,018 (17.9%)	0.00	6,754 (21.7%)	6,712 (21.6%)	0.00	10,547 (20.6%)	10,451 (20.4%)	0.00				
Hemorrhagic stroke; n (%)	0 (0.0%)	0 (0.0%)	#DIV/0!	0 (0.0%)	0 (0.0%)	#DIV/0!	84 (0.3%)	82 (0.3%)	0.00	804 (0.2%)	82 (0.2%)	0.00				

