Appendix B: Rivaroxaban vs Warfarin

Alpha blockers; n (%)	1,102 (12.3%)	1,081 (12.1%)	0.01	1,377 (12.2%)	1,405 (12.4%)	-0.01	3,766 (12.1%)	3,807 (12.3%)	-0.01	6245 (12.2%)	6293 (12.3%)	0.00
CHADS2 score, 180 days, V												
...mean (sd)	2.10 (1.19)	2.11 (1.19)	-0.01	2.19 (1.18)	2.20 (1.19)	-0.01	3.73 (1.65)	3.73 (1.64)	0.00	3.11 (1.48)	3.11 (1.48)	0.00
...median (IQR)	2.00 [1.00, 3.00]	2.00 [1.00, 3.00]	0.00	2.00 [1.00, 3.00]	2.00 [1.00, 3.00]	0.00	3.00 [3.00, 5.00]	3.00 [3.00, 5.00]	0.00	1.45 (1.65)	1.45 (1.65)	0.00
Use of Prasugrel; n (%)	25 (0.3%)	24 (0.3%)	0.00	40 (0.4%)	30 (0.3%)	0.02	**	**	#VALUE!	#VALUE!	#VALUE!	#VALUE!
Use of Loop Diuretics+other diuretics+other hyperten:	3,023 (33.8%)	3,035 (33.9%)	0.00	3,753 (33.2%)	3,790 (33.5%)	-0.01	13,931 (44.8%)	14,150 (45.5%)	-0.01	20707 (40.4%)	20975 (40.9%)	-0.01
Commercial vs Medicare Advantage- Business Type Code - CORRECT ONE - OPTUM							0	0				
...Commercial; n (%)	1461 (16.3%)	1463 (16.3%)	0.00	9,248 (81.8%)	9,258 (81.9%)	0.00	-	-	#VALUE!	10,709 (52.9%)	10,721 (52.9%)	0.00
...Medicare Advantage; n (%)	7,489 (83.7%)	7487 (83.7%)	0.00	2,052 (18.2%)	2,042 (18.1%)	0.00	-	-	#VALUE!	9,541 (47.1%)	9,529 (47.1%)	0.00
Commercial vs Medicare Advantage- Business Type Code												
...COM = COMMERCIAL; n (%)	1,461 (16.3%)	1,463 (16.3%)	0.00	-	-	#VALUE!	-	-	#VALUE!	1,461 (16.3%)	1,463 (16.3%)	0.00
...MCR = MEDICARE; n (%)	7,489 (83.7%)	7,487 (83.7%)	0.00	-	-	#VALUE!	-	-	#VALUE!	7,489 (83.7%)	7,487 (83.7%)	0.00
...MCD = MEDICAID; n (%)	0 (0.0%)	0 (0.0%)	#DIV/0!	-	-	#VALUE!	-	-	#VALUE!	0 (0.0%)	0 (0.0%)	#DIV/0!
...NONE = NO BUSINESS LINE CODE (added in 2015); n (0 (0.0%)	0 (0.0%)	#DIV/0!	-	-	#VALUE!	-	-	#VALUE!	0 (0.0%)	0 (0.0%)	#DIV/0!
...UNK = UNKNOWN (added in 2015); n (%)	0 (0.0%)	0 (0.0%)	#DIV/0!	-	-	#VALUE!	-	-	#VALUE!	0 (0.0%)	0 (0.0%)	#DIV/0!
Commercial vs Medicare Advantage- Data Type					0	0	-	-				
...1 - Fee For Service; n (%)	-	-		1,803 (16.0%)	1,817 (16.1%)	-	-	-		1,803 (16.0%)	1,817 (16.1%)	0.00
...2 - Encounter; n (%)	-	-		249 (2.2%)	225 (2.0%)	-	-	-		249 (2.2%)	225 (2.0%)	0.00
...3 - Medicare; n (%)	-	-		8,539 (75.6%)	8,523 (75.4%)	-	-	-		8,539 (75.6%)	8,523 (75.4%)	0.00
...4 - Medicare Encounter; n (%)	-	-		709 (6.3%)	735 (6.5%)	-	-	-		709 (6.3%)	735 (6.5%)	0.00
Metropolitan Statistical Area - Urban (any MSA) vs Rural (non-MSA)										0	0	0.00
...Urban; n (%)	-	-		8,353 (73.9%)	8,402 (74.4%)	-	-	-		8,353 (73.9%)	8,402 (74.4%)	0.00

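### Inclusion 4 and the stroke-history covariate count arterial occlusion or stenosis without infarction as prior ischemic stroke, although the plan's own outcome definition excludes those codes

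*Combined protocol and SAP*

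**What the plan says.** **The trial criterion.** Appendix A, Inclusion 4, gives it as "History of prior ischemic stroke, TIA or non-CNS systemic embolism believed to be cardioembolic in origin". The row above sets the logic: "It is either A) History of ischemic stroke or TIA or arterial embolism -OR- B) 2 of the following 4", the four being heart failure, hypertension, age 75 or over, and diabetes. A record under route A is enough on its own.

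**The claims implementation.** Prior ischemic stroke is "Ischemic stroke: ICD-9 diagnosis: 433.x, 434. x, 436.xx", with no restriction on the fifth digit. The window and setting are "Measured any time prior to and including day of drug initiation in any diagnosis position and inpatient or outpatient care setting".

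**The outcome.** The Primary Outcome row of Appendix A limits the same families to "433.x1 Occlusion and stenosis of precerbral arteries with cerebral infarction 434.xx (excluding 434.x0) Occlusion and stenosis of cerebral arteries with cerebral infarction", plus 436.

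**The covariate.** Appendix B lists "Ischemic stroke (w and w/o mention of cerebral infarction); n" as its ischemic-stroke row. The row for any stroke has identical counts in Optum and MarketScan. Section 9 puts the complete covariate list, apart from laboratory values, into the propensity score (PS).

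Exclusion 3a also uses unrestricted 433 and 434 codes, but only as an inpatient primary diagnosis.

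**The concern.** The plan separates infarction from occlusion or stenosis without infarction when it counts outcomes, and drops that distinction when it decides who enters and what is adjusted for. Two things are at stake.

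1. **Emulation.** Section 5.2.2 says the trial criteria were followed as closely as possible. Arterial stenosis without infarction is not an ischemic stroke, a TIA or a systemic embolism, yet one such code passes a patient who has fewer than two of the four risk factors. A closer code list already stands in the same appendix.
2. **Confounding.** The outcome is stroke, so prior infarction is a natural confounder. The only ischemic-stroke covariate mixes it with stenosis. The flag differed before matching (18.6% warfarin, 21.1% rivaroxaban, pooled). Matching can balance the mixture while its infarction part stays uneven.

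**Working it through.** **1. Code lists side by side**

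| Use | 433 family | 434 family | Position and setting |
|---|---|---|---|
| Primary outcome | 433.x1 only | all except 434.x0 | primary, inpatient |
| Inclusion 4, route A | all | all | any, inpatient or outpatient |
| Appendix B covariate | with and without infarction (label) | with and without infarction (label) | not stated |

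It follows from the rule alone that a 433 code other than 433.x1, or a 434.x0 code, with 0 or 1 risk factors, passes Inclusion 4. No passage gives a reason for the broader list or tests it.

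**2. Size of the covariate**

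Matched, pooled: 10,547 warfarin + 10,451 rivaroxaban = 20,998; 20,998 / 102,636 = 20.5%.

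**3. How many enter below the floor**

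The flowchart in Section 5.3 shows Inclusion 4 as one line (13,297, 16,046 and 36,136 removed; 19.0%, 20.4% and 16.6% of those reaching it), not split by route or fifth digit. The number is therefore not in the documents. The following is an illustration only.

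Inputs are the matched proportions in Appendix B, both arms combined. Assumptions: the four risk factors are independent of each other and of the stroke flag, and TIA and embolism are ignored. With p the proportion for each factor,

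P(0 or 1 of 4) = Π(1 − p) × [1 + Σ p/(1 − p)].

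| | Age ≥75 | Hypertension | Heart failure | Diabetes | P(0 or 1) | Stroke flag | Product | Patients |
|---|---|---|---|---|---|---|---|---|
| Optum (17,900) | 0.653 | 0.868 | 0.265 | 0.345 | 0.228 | 0.195 | 4.4% | 794 |
| MarketScan (22,600) | 0.607 | 0.771 | 0.238 | 0.317 | 0.313 | 0.179 | 5.6% | 1,267 |
| Medicare (62,136) | 0.745 | 0.944 | 0.376 | 0.445 | 0.110 | 0.217 | 2.4% | 1,478 |

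The total is about 3,540, or 3.4% of 102,636. The non-infarction share of these codes is not given. At 25%, 50% and 75% it yields about 885, 1,770 and 2,650 patients, that is 0.9%, 1.7% and 2.6%.

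The assumptions err in both directions. Ignoring TIA and embolism overstates the number. Inclusion 4 itself forces patients without a route A record to have two factors, so flag carriers may have fewer than average, which would understate it. The covariate windows also differ from those of Inclusion 4.

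**4. Power**

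The plan's figure comes first. Events = 102,636 × 10.08/1,000 = 1,034.57. Power = Φ(√(events/4) × |ln HR| − 1.96).

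- Superiority, HR 0.79: √258.64 = 16.08; 16.08 × 0.2357 − 1.96 = 1.83; power 0.966, as stated in Section 10.
- Non-inferiority, margin 1.46: 16.08 × 0.3784 − 1.96 = 4.13; power 0.99998, as stated.

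Removing 1%, 2%, 5% or 10% of events gives superiority power of 0.965, 0.964, 0.959 or 0.949. Non-inferiority power stays above 0.999.

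**The case against.** **Sensitivity at entry.** An outcome needs specificity, and the plan cites predictive values for its outcome codes. A history criterion may reasonably favour sensitivity. Row 4 lists sources in its rationale column that cannot be checked here. It also omits the late-effects codes (438, I69) used in Exclusion 3a, so narrowing 433 and 434 alone would lose genuine old strokes. This stands, and it shapes the fix. It does not explain why codes that by the plan's own reading lack infarction should suffice alone.

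**Other covariates.** TIA, late effects of cerebrovascular disease (4.9% in both arms), other cerebrovascular disease, cerebrovascular procedures and systemic embolism are listed and balanced within about 0.03. This stands in part: they reduce the confounding concern, but none isolates prior infarction. No residual imbalance is shown either.

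**ICD-10.** Those lists sit outside the document. They were mapped from the ICD-9 lists, so the breadth probably carries over, but this cannot be verified.

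**A stronger reading that fails.** A reader might infer from "CHADS2 score, 180 days, V", whose lower quartile is 1 in Optum and MarketScan, that a quarter of those patients (0.25 × 40,500 ≈ 10,100) lie below the floor because of these codes. The documents do not support this:

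- The score uses 180 days and its codes are not given. Inclusion 4 looks back any time for stroke, TIA, embolism, heart failure and diabetes. Look-back alone could explain the quartile.
- At least 25% is a minimum for scores of 0 or 1. It is neither an estimate nor an upper bound for the code problem.
- 10,100 exceeds all matched Optum and MarketScan patients carrying the broad flag in Appendix B: 1,763 + 1,721 + 2,030 + 2,018 = 7,532.

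**Conclusion.** The point holds as a definitional inconsistency with two consequences: some patients can enter who do not meet the trial criterion, and the main stroke-history covariate is a mixture.

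The number below the floor is unknown and probably a low single-digit percentage. About 70% of matched patients are in the oldest age band and about 89% carry the hypertension covariate, so most qualify through two risk factors. The range of 0.9% to 2.6% rests on the independence assumptions and on an assumed non-infarction share of 25% to 75%.

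Two further inferences should not be drawn. Power is not threatened: losing 10% of events still leaves 0.949 for superiority. Nor do the documents show a biased hazard ratio: a diluted event rate does not by itself bias it, and no difference in effect by qualifying route is shown.

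**What to change.** 1. Split the PS covariate in two: prior ischemic stroke with infarction (433.x1, 434 without 434.x0, 436, and the mapped ICD-10 codes), and occlusion or stenosis without infarction. This loses no eligible patients.
2. Align the Inclusion 4 stroke codes with the infarction-restricted list, and consider adding the plan's late-effects codes (438, I69) so that genuine old strokes are kept. At minimum, justify the broad list and add a sensitivity analysis excluding patients who qualify only through non-infarction codes.
3. Report Inclusion 4 attrition by qualifying route, and rerun the cohort, balance and power tables.

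The cost is a code-list edit and a rerun, a small loss of patients, and some sensitivity for old strokes. The comparative-analysis entries in Section 13 are still blank, so this can be settled before results are seen.

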Appendix A

4b	
– Hypertension (defined as use of antihypertensive medications within 6 months before the screening visit or persistent systolic blood pressure above 140 mmHg or diastolic blood pressure above 90 mmHg)
	
Measured 180 days prior to and including day of drug initiation in any diagnosis position and inpatient or outpatient care setting:
 
Hypertension: ICD-9 diagnosis: 401.x – 405.x
 
Plus following medication use within 6 months: Refer to the 'Hypertension meds' sheet for list of medications
	
Patorno, Elisabetta et al. "Cardiovascular outcomes associated with canagliflozin versus other non-gliflozin antidiabetic drugs: population based cohort study." BMJ 2018;360:k119 http://dx.doi.org/10.1136/bmj.k119
 
Patorno, Elisabetta et al. "Empagliflozin and the Risk of Heart Failure Hospitalization in Routine Clinical Care: A First Analysis from the Empagliflozin Comparative Effectiveness and Safety (EMPRISE) Study." Circulation. 2019 Apr 8. doi: 10.1161/CIRCULATIONAHA.118.039177

4c	– Age ≥75 years	
Measured at the time of drug initiation: Age ≥75 years
	
4d	
– Diabetes mellitus (defined as a history of type 1 or type 2 diabetes mellitus or use of antidiabetic medications within 6 months before screening visit)
	
Measured any time prior to and including day of drug initiation in diagnosis position and inpatient or outpatient care setting:
 
DM type 2: ICD-9 diagnosis: 250.x0 or 250.x2 ICD-10 diagnosis: E11.x
 
DM type 1: ICD-9 diagnosis: 250.x1 or 250.x3 ICD-10 diagnosis: E10.x
 
-OR-
 
Following drug dispensing within 6 months of drug initiation: Refer to the 'Diabetes meds' sheet for list of DM Drugs
	
Patorno, Elisabetta et al. "Cardiovascular outcomes associated with canagliflozin versus other non-gliflozin antidiabetic drugs: population based cohort study." BMJ 2018;360:k119 http://dx.doi.org/10.1136/bmj.k119
 
Patorno, Elisabetta et al. "Empagliflozin and the Risk of Heart Failure Hospitalization in Routine Clinical Care: A First Analysis from the Empagliflozin Comparative Effectiveness and Safety (EMPRISE) Study." Circulation. 2019 Apr 8. doi: 10.1161/CIRCULATIONAHA.118.039177

5	
Female subjects must be postmenopausal (for at least 2 years), surgically sterile, abstinent, or, if sexually active, be practicing an effective method of birth control (e.g., prescription oral contraceptives, contraceptive injections, intrauterine device, double-barrier method, contraceptive patch, male partner sterilization) before entry and throughout the study; and, for those of childbearing potential, have a negative serum β-hCG pregnancy test at screening.
	N/A	We will incorporate this by excluding 'pregnant' women below.
6	Subjects must have signed an informed consent document indicating that they understand the purpose of and procedures required for the study and are willing to participate in the study	N/A	
7	In order to participate in the optional pharmacogenomic component, subjects must have signed the informed consent for DNA research document indicating willingness to participate in the pharmacogenomics component of the study (where local regulations permit)	N/A	
EXCLUSION CRITERIA			
1	Cardiac-Related Conditions		
1a	Hemodynamically significant mitral valve stenosis	
Measured 180 days prior to and including day of drug initiation in any diagnosis position and inpatient or outpatient care setting:
 
Mitral stenosis: ICD-9 diagnosis: 396.0x, 396.1x ICD-10 diagnosis: I34.2x, I05.1x, I05.2x
	
1b	Prosthetic heart valve (annuloplasty with or without prosthetic ring, commissurotomy and/or valvuloplasty are permitted)	
Measured 180 days prior to and including day of drug initiation in any diagnosis position and inpatient or outpatient care setting:
 
ICD-9 diagnosis: V43.3x ICD-10 diagnosis: Z95.2x
 
CPT procedure: (TAVR with prosthetic valve) 33361, 33362, 33363, 33364, 33365, 33366, 33367, 33368, 33369, 33477, 0483T, 0484T, 0569T, 0570T
	
1c	Planned cardioversion (electrical or pharmacological)	N/A	Will not capture 'planned' procedures
1d	Transient atrial fibrillation caused by a reversible disorder (e.g., thyrotoxicosis, PE, recent surgery, MI)	N/A	Transient AF would not be well captured in claims.
1e	Known presence of atrial myxoma or left ventricular thrombus	
Measured 180 days prior to and including day of drug initiation in any diagnosis position and inpatient or outpatient care setting:
 
Atrial myxoma: ICD-9 diagnosis: 212.7 (Benign neoplasm of heart) ICD-10 diagnosis: D15.1 (Benign neoplasm of heart)
 
Left ventricular thrombus: ICD-10 diagnosis: I51.3 (Intracardiac thrombosis)
	Joshi, Kirti K et al. "Postoperative atrial fibrillation in patients undergoing non-cardiac non-thoracic surgery: A practical approach for the hospitalist." Hospital practice (1995) vol. 43,4 (2015): 235-44. doi:10.1080/21548331.2015.1096181

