...median [IQR]	0.00 [0.00, 0.00]	0.00 [0.00, 0.00]	0.00	0.00 [0.00, 0.00]	0.00 [0.00, 0.00]	0.00	0.00 [0.00, 0.00]	0.00 [0.00, 0.00]	0.00	0.00 (0.63)	0.00 (0.64)	0.00
Number of Cardiac biomarkers tests (tropnin, CK-MBs, Myoglobin, CPK)												
...mean (sd)	0.45 (1.43)	0.49 (1.47)	-0.03	0.32 (1.24)	0.39 (1.40)	-0.05	0.36 (0.71)	0.41 (0.73)	-0.07	0.37 (1.00)	0.42 (1.06)	0.00
...median [IQR]	0.00 [0.00, 0.00]	0.00 [0.00, 0.00]	0.00	0.00 [0.00, 0.00]	0.00 [0.00, 0.00]	0.00	0.00 [0.00, 1.00]	0.00 [0.00, 1.00]	0.00	0.00 (1.26)	0.00 (1.37)	0.00
Number of Ambulatory Blood pressure monitoring tests												
...mean (sd)	0.00 (0.04)	0.00 (0.04)	0.00	0.00 (0.03)	0.00 (0.04)	0.00	0.00 (0.03)	0.00 (0.04)	0.00	0.00 (0.03)	0.00 (0.04)	0.00
...median [IQR]	0.00 [0.00, 0.00]	0.00 [0.00, 0.00]	0.00	0.00 [0.00, 0.00]	0.00 [0.00, 0.00]	0.00	0.00 [0.00, 0.00]	0.00 [0.00, 0.00]	0.00	0.00 (0.04)	0.00 (0.05)	0.00
N of days on antihypertensive medications during baseline												
...mean (sd)	139.61 (62.26)	137.95 (63.30)	0.03	139.79 (63.30)	139.00 (63.70)	0.01	147.57 (55.78)	147.35 (55.84)	0.00	144.47 (58.67)	143.87 (58.99)	0.00
...median [IQR]	174.00 [123.00, 181.00]	174.00 [117.00, 181.00]	0.00	176.00 [125.00, 181.00]	175.00 [121.00, 181.00]	0.02	176.00 [144.00, 181.00]	176.00 [144.00, 181.00]	0.00	107.85 (70.61)	107.63 (71.01)	0.00
N of days in database anytime prior												
...mean (sd)	2,041.05 (1,371.23)	2,042.84 (1,399.19)	0.00	2,552.38 (1,366.73)	2,530.20 (1,365.03)	0.02	811.15 (547.72)	817.84 (520.25)	-0.01	1409.06 (959.60)	1408.54 (956.85)	0.00
1,782.50 [856.75, 1,747.50 [822.00,												
...median [IQR]	3,039.00]	3,082.00]		0.03 [8.50 [1,338.00, 3,690.00]	34.00 [1,285.00, 3,667.00]		0.01 [634.00 [462.00, 963.00]	649.00 [484.00, 971.00]	-0.03	1022.66 (1280.79)	1016.66 (1278.03)	0.00
Mean Copay for per prescription cost (charges in U.S. \$)(180-1 day prior)												
...mean (sd)	29.02 (37.48)	29.19 (41.67)	0.00	18.71 (20.72)	18.78 (20.05)	0.00	117.00 (89.10)	118.16 (110.23)	-0.01	80.01 (71.73)	80.76 (88.02)	0.00
...median [IQR]	18.33 [7.69, 36.56]	18.77 [8.00, 35.85]	-0.01	14.04 [6.59, 24.85]	14.11 [6.77, 25.00]	0.00	95.83 [68.28, 137.63]	95.81 [68.80, 135.71]	0.00	27.39 (72.88)	27.48 (88.90)	0.00
...Missing; n (%)	194 (2.2%)	201 (2.2%)	0.00	227 (2.0%)	242 (2.1%)	-0.01	403 (1.3%)	429 (1.4%)	-0.01	824 (1.6%)	872 (1.7%)	-0.01

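### Exclusion 1b looks for a prosthetic heart valve only in the 180 days up to index, so valves coded only earlier stay in a cohort meant to be non-valvular AF.

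*Combined protocol and SAP*

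**What the plan says.** The trial criterion in Appendix A, row 1b, reads "Prosthetic heart valve (annuloplasty with or without prosthetic ring" and goes on to list permitted valve procedures. It sets no time window. The claims version is "Measured 180 days prior to and including day of drug initiation in any diagnosis position and inpatient or outpatient care setting"; the same sentence appears in several other rows, and here it is row 1b that matters. The codes are "ICD-9 diagnosis: V43.3x ICD-10 diagnosis: Z95.2x" plus a CPT list labelled as TAVR.

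Row 1a (hemodynamically significant mitral stenosis) has the same 180-day window and diagnosis codes only: "Mitral stenosis: ICD-9 diagnosis: 396.0x, 396.1x ICD-10 diagnosis: I34.2x, I05.1x, I05.2x".

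Other rows look back further. Prior ischemic stroke, TIA or systemic embolism under inclusion 4 is "Measured any time prior to and including day of drug initiation in any diagnosis position and inpatient or outpatient care setting". The lead-in to the inclusion 4 risk factors, which covers heart failure, is also any-time, and diabetes (4d) is "Measured any time prior to and including day of drug initiation in diagnosis position". AF itself uses 12 months, hypertension (4b) uses 180 days, and every exclusion with a stated window uses 180 days or less.

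Section 5.1 requires 180 days of continuous enrollment, and Section 5.2 defines new use by 180 days without use. Section 5.2.2 undertakes to follow the trial's criteria as nearly as possible. Appendix B reports "N of days in database anytime prior" by arm.

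**The concern.** A prosthetic valve does not lapse after six months. Where the trial wanted a window it stated one, for example 30 days and 6 months in 2b and 3 months and 14 days in 3a. For 1b it stated none, and the row gives no reason for adding one. Because the procedure list is labelled TAVR, a surgical valve implanted earlier is found only if a status code was recorded within the 180 days.

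Two things are at stake. The first is the definition of the population, since any valve that is missed contradicts non-valvular AF. The second is confounding. Section 5.2.1 describes rivaroxaban's approval as for non-valvular AF, so missed valve patients might be found more often on warfarin. If they also have more strokes or emboli, the hazard ratio falls towards the trial's 0.79, and in a replication that error would look like agreement. Appendix B has no row for prosthetic valve or mitral stenosis, so the balance tables would not reveal it.

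**Working it through.** **1. The plan's own figures.** The flowchart rows in Section 5.3 subtract correctly. Removed by 1b, arms combined:
- Optum: 1,238 / 56,369 = 2.20%
- MarketScan: 789 / 62,380 = 1.26%
- Medicare: 3,016 / 181,111 = 1.67%
- Together: 5,043 / 299,860 = 1.68%

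Pooled expected events in Section 10 are 102,636 × 10.08 / 1,000 = 1,034.57. With 1:1 allocation, power = Φ(½√D · |ln HR| − 1.96). At D = 1,034.57 and HR 0.79 this is Φ(16.08 × 0.2357 − 1.96) = 0.966, as stated.

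**2. How much history goes unused.** Mean days in the database after matching (Appendix B), warfarin / rivaroxaban:
- Optum: 2,041 / 2,043, so 180 days is about 9%
- MarketScan: 2,552 / 2,530, about 7%
- Medicare: 811 / 818, about 22%

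**3. Possible bias.** The documents give no valve count beyond 180 days and none by arm, so this step rests on assumed inputs. Let p_W and p_R be the residual valve prevalence on warfarin and rivaroxaban, and r the event-rate ratio of valve to non-valve patients. Then apparent HR / true HR = [1 + p_R(r − 1)] / [1 + p_W(r − 1)].

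With p_R = 0:

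| p_W | r = 2 | r = 3 | r = 4 |
|---|---|---|---|
| 0.2% | 0.998 | 0.996 | 0.994 |
| 1% | 0.990 | 0.980 | 0.971 |
| 2% | 0.980 | 0.962 | 0.943 |

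In the matched warfarin arm, 0.2% of 51,318 is about 103 patients and 2% is about 1,026. If the residue were half as common on rivaroxaban, the worst cell would be 1.03 / 1.06 = 0.972. If it were equal in both arms, the factor would be 1.

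**4. Scale.** The approximate standard error of the pooled log HR is 2/√1,034.57 = 0.062. The worst cell shifts the log HR by ln(1/1.06) = −0.058, just under one standard error. To turn a true HR of 1.00 into 0.79, p_W would have to be (1/0.79 − 1)/(r − 1): 27% at r = 2, 13% at r = 3 and 9% at r = 4.

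**5. Cost in power.** The number of extra exclusions cannot be computed. For an assumed 5% loss, D = 982.84 and superiority power is Φ(15.675 × 0.2357 − 1.96) = 0.959. Non-inferiority power stays above 0.9999.

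**The case against.** The case for leaving 180 days in place has real substance.

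- *It is the standard window.* A reader might infer that the valve rows are an exception to an otherwise all-history plan. They are not. Any-time look-back applies only to some inclusion 4 items, and 180 days matches the guaranteed enrollment, which gives every patient the same minimum observation. This stands. It shows the choice is consistent, but not that it suits a lasting condition with no trial window.

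- *New-user design and matching already remove many such patients.* Prior warfarin use removes 482,398 (Optum), 622,538 (MarketScan) and 2,080,069 (Medicare) before the valve step. The pooled mean number of INR tests in the warfarin arm falls from 3.13 before matching to 0.41 after, against 0.39 on rivaroxaban. Many established warfarin users are therefore gone. The washout also looks back only 180 days, however, so a patient restarting after a longer gap can re-enter.

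- *Adjustment may be partial.* It is tempting to say that the propensity score cannot correct the leak. The documents do not support that: the content of the Other CVD covariate is not given, and INR-test counts may act as a proxy. No covariate addresses valves directly.

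- *Direction is unproven.* A reader might also infer that missed valve patients are shown to sit in the warfarin arm. They are not. It is an inference from the approval wording in Section 5.2.1.

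- *Any-time search is not neutral between arms.* Exclusions are applied before matching, when mean Medicare history is 953 days on warfarin and 824 on rivaroxaban (St. Diff. 0.22), with smaller differences the other way in Optum and MarketScan. The near-equal 811 and 818 days describe patients already matched. This stands as a cost of the change.

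- *Mitral stenosis differs.* Criterion 1a concerns hemodynamically significant stenosis. Old diagnosis codes could remove patients whose stenosis was never significant or has been treated. This stands, so 1a should not be changed outright.

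**Conclusion.** The point holds for exclusion 1b. The window is narrower than the trial criterion, the plan already accepts all-history search for other items, and mean available history is several times 180 days in every database. Known prosthetic valves can therefore remain in a cohort meant to exclude them, and the planned tables would not show how many or in which arm.

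The likely effect on the hazard ratio is small. The 0.998 to 0.943 range assumes a 0.2-2% residue, all on warfarin, with 2-4 times the event rate, and no figure in the documents supports any of these three inputs. Even the extreme is below one standard error at the planned pooled event count, and by itself could not produce 0.79 from a true value of 1.00. The reason to act is that the fix is specific and cheap and brings the cohort closer to the trial population; the documents do not show that the main result would change. For 1a the longer window is a trade-off, not a clear correction.

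**What to change.** For 1b, replace the 180-day window with all available data up to and including the index date, rerun the cohort and matching, and report any-time prosthetic-valve codes by arm before and after matching. For 1a, keep the current window in the main analysis and run the all-history search as a sensitivity analysis.

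The cost is one definition change, one rerun in each database and a loss of patients that should be small. Because look-back length differs by arm before matching, its balance must be rechecked after rematching. The date for the comparative analyses in Section 13 is blank, so on this document the change can still be made before outcome results are seen.
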